6.2 Safety Variables

Safety endpoints such as AEs, laboratory tests, vital signs, ECGs and ECOG performance status are secondary endpoints of the study.

Safety will be assessed by evaluation of the following variables:

- Treatment-emergent adverse events (TEAEs; frequency, severity, seriousness, and relationship to study drug).
 - TEAE is defined as an adverse event observed after starting administration of the study drug. If the adverse event occurs on Day 1 and the onset check box is marked "Onset after first dose of study drug" or the onset check box is left blank, then the adverse event will be considered treatment emergent. If the adverse event occurs on Day 1 and the onset check box is marked "Onset before first dose of study drug", then the adverse event will not be considered treatment emergent. If a subject experiences an event both during the pre-

investigational period and during the investigational period, the event will be considered as TEAE only if it has worsened in severity (i.e. it is reported with a new start date). All adverse events collected that begin within 30 days after taking the last dose of study drug will also be counted as TEAE. Any AEs with onset dates completely missing will be considered TEAEs in summaries. AEs with partially missing onset dates will be assumed TEAEs unless the available portion of the date indicates that the onset was strictly before start of study medication.

- A drug-related TEAE is defined as any TEAE with at least possible relationship (possibly or probably related) to study treatment as assessed by the investigator or with missing assessment of the causal relationship
- Serious adverse events (SAEs) include adverse events that are flagged as serious by the investigator on eCRF, or upgraded by the Sponsor based on review of the Sponsor's list of Always Serious term.
- Clinical laboratory variables

Below is a table of the laboratory tests that will be performed during the conduct of the study. Refer to the Schedule of Assessments for study visit collection dates.

Additional laboratory tests should be performed according to institutional standard of care. Clinical significance of out-of-range laboratory findings is to be determined and documented by the investigator or delegated sub-investigator who is a qualified physician.

Table 3 Laboratory Assessments

Panel/Assessment	Parameters to be analyzed	NCI-CTCAE
		Grading
		(Hyper/Hypo)
Hematology	Hematocrit (Hct)	N/A
	Hemoglobin (Hgb)	Both
	Red Blood Cell Count (RBC)	N/A
	White Blood Cell Count (WBC)	Both
	WBC differential	N/A
	Platelets	Нуро
	Mean Corpuscular Volume (MCV)	N/A
	Mean Corpuscular Hemoglobin (MCH)	N/A
	Mean Corpuscular Hemoglobin Concentration (MCHC)	N/A
Table continued on nex	rt page	·

Panel/Assessment	Parameters to be analyzed	NCI-CTCAE
	·	Grading
		(Hyper/Hypo)
Biochemistry (fasting)	Sodium (Na)	Both
- · · · · · · · · · · · · · · · · · · ·	Magnesium (Mg)	Both
	Creatine Phosphokinase (CK)	Hyper
	Potassium (K)	Both
	Calcium (Ca)	Both
	Chloride (Cl)	N/A
	Phosphate (P)	Нуро
	Creatinine (Cr)	Hyper
	Glucose (Gl)	Both
	Blood Urea Nitrogen (BUN)	N/A
	Alkaline Phosphatase (ALP)	Hyper
	Aspartate Aminotransferase (AST)	Hyper
	Alanine Aminotransferase (ALT)	Hyper
	Lactate Dehydrogenase (LDH)	N/A
	Bilirubin Total (TBL) (total and direct)	Hyper
	Total Protein (TP)	N/A
	Albumin (Alb)	Нуро
	Bicarbonate (HCO3)	N/A
	Serum HCG for female subjects of childbearing	N/A
	potential	
Urinalysis	Protein	N/A
	Glucose	N/A
	pН	N/A
	Occult Blood	N/A
	Ketones	N/A
	Bilirubin	N/A
	Urobilinogen	N/A
	Sodium	N/A
	Potassium	N/A
	Chloride	N/A
Coagulation Profile	PT (sec)	N/A
	APTT	Hyper
	INR	Hyper

- Vital signs (systolic and diastolic blood pressures (mmHg), radial pulse rate (beats/minute) and body temperature)
- 12-lead electrocardiogram (ECG)
- ECOG performance scores
- Physical Examination Standard(general appearance, skin, eyes, ears, nose, throat, neck, cardiovascular, chest and lungs, abdomen, musculoskeletal, neurologic status, mental status, and lymphatic systems)

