7.10 Handling of Missing Data, Outliers, Visit Windows, and Other Information

As a general principle, no imputation of missing data will be done. Exceptions are the start and stop dates of AEs and concomitant medication. The imputed dates will be used to allocate the concomitant medication and AEs to a treatment group, in addition to determining whether an AE is/is not treatment-emergent. Listings of the AEs and concomitant medications will present the actual partial dates; imputed dates will not be shown.

Subjects with missing overall response assessment will be regarded as nonresponders in ORR analysis.

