7.10 Handling of Missing Data, Outliers, Visit Windows, and Other Information

7.10.1 Missing Data

Every effort will be made to resolve missing or incomplete dates for adverse events and concomitant medications. If a partial date cannot be resolved, the most conservative imputation methods will be used to complete the missing information.

Missing or partial start and stop dates of adverse events, non-medication therapy and concomitant medication will be imputed using the following algorithm:

- Imputation rules for partial or missing stop dates:
 - o If the month and year are present, then impute as the last day of that month.
 - o If only the year is present, impute as December 31 of that year.
 - o If the stop date is entirely missing, assume the event or medication is ongoing.
- Imputation rules for partial or missing start dates:

		Stop Date						
		Complete: yyyymmdd		Partial:	Partial: yyyymm		Partial: yyyy	
Star	t Date	< 1 st dose	≥ 1 st dose	< 1 st dose yyyymm	≥ 1 st dose yyyymm	< 1 st dose	≥ 1 st dose yyyy	
Partial:	= 1 st dose yyyymm	2	1	2	1	n/a	1	1
уууутт	≠ 1 st dose yyyymm	2	2	2	2	2	2	2
Partial:	$= 1^{st} dose$ $yyyy$	3	1	3	1	n/a	1	1
уууу	$\neq 1^{st}$ dose $yyyy$	3	3	3	3	3	3	3
Mi	ssing	4	1	4	1	4	1	1

^{1 =} Impute as the date of first dose; 2 = Impute as the first of the month; 3 = Impute as January 1 of the year;

The imputed dates will be used to determine whether an AE is/is not treatment emergent. Listings of AEs, non-medication therapy and concomitant medications will present the actual partial dates; imputed dates will not be shown.

For secondary endpoint OS, missing or incomplete death date will be imputed as the earliest feasible date on or after the date last known to be alive as the examples shown in the table below.

^{4 =} Impute as January 1 of the stop year

Sponsor: Astellas Pharma Global Development, Inc.

ISN/Protocol 8273-CL-0302

Incomplete Date of Death (YYYY MMM DD)	Date Last Know to be Alive (YYYY MMM DD)	Imputed Date of Death (YYYY MMM DD)
2005 APR ??	2005 MAR 31	2005 APR 01
2005 ??? 13	2005 MAR 31	2005 APR 13
2005 ??? ??	2005 MAR 31	2005 MAR 31
????? APR ??	2005 MAR 31	2005 APR 01
????? APR 13	2005 MAR 31	2005 APR 13
???? ??? ??	2005 MAR 31	2005 MAR 31

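### SAP 6.2 counts some adverse events that ended before first dose as treatment-emergent, while SAP 7.10.1 classifies the same events as not treatment-emergent

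*SAP*

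**What the plan says.** **SAP 6.2** defines a TEAE as an event seen after study drug has started, then gives two rules for incomplete onset dates. For a wholly missing onset: "Any AEs with onset dates completely missing will be considered TEAEs in summaries". For a partial onset: "AEs with partially missing onset dates will be assumed TEAEs unless the available portion of the date indicates that the onset was strictly before start", the reference point being the first dose. Neither rule refers to the stop date.

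**SAP 7.10.1** has a table headed "Imputation rules for partial or missing start dates", which crosses what is known of the onset with what is known of the stop date. The codes that matter are:
- code 1: "Impute as the date of first dose"
- code 2: first of the month
- code 3: January 1 of the year
- code 4: "Impute as January 1 of the stop year"

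It then says: "The imputed dates will be used to determine whether an AE is/is not treatment emergent". **Protocol 7.10** gives imputed dates the same purpose ("in addition to determining whether an AE is/is not treatment-emergent").

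**SAP 7.5.1** classes events from the pre-investigational period as Baseline Signs and Symptoms and builds its AE summaries on TEAEs. No section says whether 6.2 or 7.10.1 governs when they differ.

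**The concern.** Under Protocol 5.4.2, AE collection starts at informed consent, and the schedule allows screening from Day -28. An event can therefore start and finish before first dose and still be in the AE data. If its onset is incomplete but its stop date shows that it was over before dosing, 6.2 reports it as treatment-emergent and 7.10.1 does not. Two programmers who each follow the SAP could produce different TEAE counts from the same data.

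The serious, drug-related and Grade 3 or higher tables in 7.5.1 all start from this flag. The optional exposure-adjusted rates measure time from first dose to first occurrence. If the imputed onset were used there for an event that 6.2 had made a TEAE, that time would be negative.

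**Working it through.** There is no planned figure to reproduce. The check sets the two rules side by side. I read the last column of the 7.10.1 table as stop date missing. That column is not involved in the conflict.

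| Onset recorded | Stop recorded | SAP 6.2 | Onset imputed by 7.10.1 | Status under 7.10.1 |
|---|---|---|---|---|
| Missing | Before first dose (full date, month or year) | TEAE | January 1 of stop year (code 4) | Not a TEAE |
| Month of first dose only | Full date, before first dose | TEAE | First of that month (code 2) | Not a TEAE |
| Year of first dose only | Full date or month, before first dose | TEAE | January 1 of that year (code 3) | Not a TEAE |
| Any of the above | On or after first dose, or missing | TEAE | First-dose date (code 1) | TEAE, if the Day 1 box is blank or marked after first dose |
| Month or year earlier than that of first dose | Any | Not a TEAE | Code 2 or 3, before first dose | Not a TEAE |

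**Why the first three rows always conflict.** For code 4 with a full stop date, January 1 of the stop year ≤ stop date < first dose. With a stop month or year, the table requires that month or year to precede that of first dose, so January 1 of the stop year precedes first dose as well. For codes 2 and 3, if the dates are coherent the event stopped in the same month (or year) as its onset, so the first of that month (or January 1) ≤ stop date < first dose.

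**Enumeration for a wholly missing onset.** I took every first-dose date in 2016-2017 (366 + 365 = 731 days), with stop dates from 40 days before to 40 days after. The date range was chosen only for the check.
- Stop before first dose: the imputed onset was pre-dose in 29,240 of 29,240 cases with a full stop date (731 × 40), 18,466 of 18,466 with month only, and 1,640 of 1,640 with year only. SAP 6.2 gives a TEAE in all of them.
- Stop on or after first dose: the imputed onset was the first-dose date in all 29,971 full-date cases (731 × 41), all 40,745 month-only cases and all 57,571 year-only cases. The rules agree.

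**Enumeration for an onset known to the month of first dose**, with a full stop date before first dose in that month: code 2 was pre-dose in 10,774 of 10,774 cases. Year-only onsets were not enumerated. They follow from the inequality above.

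These counts show that the conflict is systematic within the first three rows. They say nothing about how often such records will occur.

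**Examples**, with first dose on 15 March 2016 and stop on 10 March 2016:
- Onset missing: 7.10.1 imputes 1 January 2016, not a TEAE. SAP 6.2 counts a TEAE.
- Onset March 2016, day unknown: 7.10.1 imputes 1 March 2016, not a TEAE. SAP 6.2 counts a TEAE.

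**Size.** The documents give no rate of screening AEs or of incomplete dates. Purely as an assumption, suppose 20-40% of 600 subjects have an AE before first dose, 2-5% of these have an incomplete onset, and half of those resolve before dosing:
- low: 600 × 0.20 × 0.02 × 0.5 = 1.2 subjects (0.2%)
- high: 600 × 0.40 × 0.05 × 0.5 = 6 subjects (1.0%)

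Even on these inputs the result is too high. It includes partial onsets in a month or year before that of first dose, on which both rules agree (last row of the table).

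**The case against.** The strongest reply is that the intended rule can be inferred. SAP 7.10.1 and Protocol 7.10 both let imputed dates decide TEAE status, the opening definition in 6.2 requires onset after dosing begins, and 7.5.1 sets pre-dose events apart. The missing-onset sentences in 6.2 would then be a fallback for when nothing else is known. This shows which answer is right, but the wording of 6.2 is unconditional and nothing marks it as subordinate. The words in 6.2 that limit it to summaries do not separate the rules either. SAP 7.10.1 shows only actual partial dates in listings, so its imputed dates serve the same summaries.

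A second reply is that 6.2 is deliberately conservative. That is sensible when timing is uncertain, but a recorded stop before first dose removes the uncertainty.

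Two points on the other side stand. SAP 7.10.1 promises every effort to resolve incomplete dates, so only records left after querying are affected. The listings also keep the actual dates, so any such record can be seen.

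Some stronger readings are not supported:
- A reader might infer that 6.2 makes every AE with an incomplete onset a TEAE. It does not. Partial onsets clearly before first dose are excluded.
- A reader might infer that the drug-related tables are notably inflated, because 6.2 counts missing causality as related. That needs an incomplete onset, a pre-dose stop and a missing causality in one record. It is a separate convention and is not evidence for this conflict.
- A reader might infer that 6.2 should simply defer to imputed dates. That would change cases not in dispute. A missing onset imputed to Day 1 could meet the Day 1 check-box rule and cease to be a TEAE. A partial onset imputed to the first of a month could fall outside the 30-day window after last dose.

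**Conclusion.** Wrong as written, and minor. For events with a recorded stop before first dose, and an onset either wholly missing or known only to the month or year of first dose, SAP 6.2 and 7.10.1 give opposite TEAE classifications. The 6.2 result is the incorrect one. Elsewhere the rules agree, apart from the Day 1 check box and the 30-day window.

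The number of events cannot be derived from the documents and is probably very small. A count of 1 to 6 subjects would rest entirely on assumed rates and would overstate the problem even on those rates. There is no evident reason for the arms to differ, since these events precede treatment. PFS, OS and type I error are untouched.

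**What to change.** Keep both missing-onset sentences in SAP 6.2 and add to them: *unless the stop date is before the first dose, using the complete, yyyymm or yyyy stop-date comparison in the Section 7.10.1 table, in which case the AE is not a TEAE.*

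This makes the first three rows of the comparison agree and leaves the other rows as they are. Tying the clause to the table's comparisons also settles a stop date known only to the month or year of first dose. The table treats that as not before first dose, so the event stays a TEAE.

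The cost is one clause in the SAP and one condition in the AE dataset program. SAP Section 1 allows revisions before database hard lock.

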6.3 Pharmacokinetics Variables

Plasma concentration data of ASP8273 and its metabolite(s) (if applicable) will be analyzed and descriptive statistics will be provided. Additional model-based analyses may be performed and reported separately.

6.4 Biomarker Variables

Tumor tissue sample (FFPE) will be obtained and sent for central confirmatory testing to evaluate for EGFR activating mutation. The sample sent for confirmatory testing should be from the same specimen as used for local testing for eligibility. A plasma sample will be collected to evaluate EGFR mutations. Plasma and whole blood samples will be collected for exploratory analysis of biomarkers. An optional post-progression tumor tissue sample for exploratory biomarker analysis may be collected following centrally confirmed disease progression for subjects who sign a separate ICF.

6.5 Quality of Life Variables

Subjects will be asked to complete the QoL and PRO questionnaires electronically at baseline and at day 1 of each cycle where a visit takes place.

6.5.1 FACT-EGFRI-18

The Functional Assessment of Chronic Illness Therapy-EGFR Inhibitors Subscale (FACT-EGFRI-18) is a treatment-specific subscale of the Functional Assessment of Chronic Illness Therapy (FACIT) measurement system specifically designed to assess the effect of EGFR inhibitors on quality of life. (Wagner et al). The FACT-EGFRI-18 is an 18-item Likert-scaled questionnaire, arranged in three HRQL dimensions: physical (seven items), social/emotional (six items), and functional well-being (five items). The instrument takes less than 10 minutes to complete, and the recall period is the past 7 days. The response scores ranged from 0 to 4, and the response categories include "not at all", "a little bit", "somewhat", "quite a bit", and "very much". Negatively worded items (e.g., "My skin bleeds easily "or "My skin condition affects my mood") are reverse-scored, so that participants who experience a higher impact of symptom burden on HRQL receive a lower score (range 0-72).

6.5.2 EORTC-QLQ-C30

The EORTC-QLQ-C30 is a 30-item cancer-specific instrument (Aaronson et al 1993). Multitrait scaling was used to create five functional domain scales: Physical, Role, Emotional, Social and Cognitive; two items evaluate global QoL; in addition, three symptom scales assess Fatigue, Pain and Emesis; and six single items assess other symptoms.

Validity for EORTC-QLQ-C30 was illustrated in a study evaluating quality of life in a sample of NSCLC patients, where the EORTC-QLQ-C30 discriminated between participants in the intervention arm (186 patients undergoing adjuvant chemotherapy) and in the observation arm (173 patients), with significant differences in the domains of Global quality of life, Physical functioning, Role functioning and Social functioning showing better scores for the observation arm at 3 months, returning to baseline score at 9 months (Bezjak et al 2008). In the most recent version of the instrument (version 3), the Cronbach's alpha-

Sponsor: Astellas Pharma Global Development, Inc.

ISN/Protocol 8273-CL-0302

coefficients for internal consistency ranged from 0.56 to 0.85, with emotional functioning having the highest Cronbach's alpha-coefficient (Cankurtaran et al 2008). The EORTC-QLQ-C30 discriminated between different types of cancers (lung, colorectal and prostate) in a study exploring peri-diagnostic and survival wait times (Grunfeld et al 2009). Predictive validity of the EORTC-QLQ-C30 was illustrated in a study with 538 cancer patients (101 had lung cancer) where Function and Symptom scales were predictive of overall patient satisfaction upon univariate analysis (Lis et al 2009).

The instrument's evidence for the ability to detect change has been reported for NSCLC treatment trials (Yang et al 2013 & O'Brien et al 2004). Evidence supporting interpretation of scores (i.e., availability of MID estimates in patients with NSCLC) also is available (Maringwa et al 2011). Like the other EORTC instruments, the recall period for items is the past 7 days, and response options include a 4-point Likert scales, yes/no options, or a 7-point scale for 2 global questions related to overall health status and HRQL. The instrument takes less than ten minutes to complete. The total score for the instrument ranges from 0 to 100, with a high score for a functional scale representing a high/healthy level of functioning and a high score for a symptom scale or item representing a high level of symptomatology or problems (Fayers et al 2001).

6.5.3 EORTC-QLQ-LC13

The EORTC-QLQ-LC13 is a validated module of the EORTC-QLQ-Core 30, developed in 1994. Module items evaluate symptoms such as cough, hemoptysis, shortness of breath, sore mouth or tongue, dysphagia, tingling hands or feet, hair loss and pain. The developers of EORTC-QLQ-LC13 indicate that it is highly preferred not to use the LC13 alone (without the core module QLQ-C30), since the module has been designed to be used together with the core questionnaire, and the content validity is based upon this combination. The response options and scoring system are the same as for the EORTC QLQ-C30, and the administration is similar. The recall period for items is the past 7 days, and response options include either a 4-point Likert scale or yes/no options. The instrument takes less than ten minutes to complete. The total score for the instrument ranges from 0 to 100. A high score for a functional scale represents a high/healthy level of functioning whereas a high score for a symptom scale or item represents a high level of symptomatology or problems (Fayers et al 2001).

6.5.4 EQ-5D-5L

The EQ-5D is a generic preference-based measure that indirectly measures the utility for health that generates an index-based summary score based upon societal preference weights (Pickard et al 2007). The EQ-5D-5L consists of 6 items that cover 5 main domains (mobility, self-care, usual activities, pain/discomfort, and anxiety/depression) and a general visual analog scale for health status. The utility scores allow for comparisons of disease burden to be made across various conditions, and the calculated quality-adjusted life years as an outcome for determining the cost effectiveness of health care interventions. The index-based score is typically interpreted along a continuum where 1 represents best possible health and 0 represents dead.

Sponsor: Astellas Pharma Global Development, Inc.

ISN/Protocol 8273-CL-0302

6.6 Other Variables

• Body Mass Index (BMI)

BMI = weight (kg) / $[height (m)]^2$

• Duration of exposure

Duration of exposure to a study drug will be calculated in days, using the following formula:

(Date of last dose of study drug – Date of first dose) + 1 When the start or stop date is missing, then the exposure will be treated as missing.

• Cumulative Actual Dose

Total amount of study drug actually taken by the patient from first dose date to last dose date

Planned Dose Intensity

Planned dose intensity for ASP8273 is 300 mg/day, for erlotinib is 150 mg/day and for gefitinib is 250 mg/day.

• Actual Dose Intensity

Defined as the cumulative actual dose divided by duration of exposure

• Relative Dose Intensity (RDI)

```
Actual Dose Intensity
----- x 100
Planned Dose Intensity
```

Duration of NSCLC

Duration of NSCLC will be calculated in days using the following formula:

```
(Randomization date – date of initial diagnosis of NSCLC) + 1
```

If the date of initial diagnosis of NSCLC is incomplete or missing, then the duration of NSCLC will be missing.

• Duration of NSCLC since date of locally advanced or metastatic disease diagnosis

Duration of NSCLC since date of locally advanced or metastatic disease diagnosis will be calculated in days using the following formula:

(Randomization date – date of locally advanced or metastatic disease diagnosis) + 1

If the date of locally advanced or metastatic disease diagnosis is incomplete or missing, then the duration of NSCLC since date of locally advanced or metastatic disease diagnosis will be missing.

Previous and concomitant medication

Previous medication is defined as medication with at least one dose taken before the date of the first dose of study drug.

Concomitant medication is defined as medication with at least one dose taken between the date of first dose (inclusive) and the date of last dose (inclusive) of study drug.

Previous and concomitant non-medication therapy

Previous non-medication therapy is defined as non-medication therapy administered at least once before the date of the first dose of study drug.

Concomitant medication is defined as non-medication therapy administered at least once between the date of first dose (inclusive) and the date of last dose (inclusive) of study drug.

